2.0 TRIAL DESIGN

2.1 Trial Design

This is a single center, open label trial of pembrolizumab in patients failing to respond to or relapsing after anti-CD19 chimeric antigen receptor modified T cell therapy (CTL019/CTL119) for relapsed or refractory CD19+ lymphomas.

Eligible patients will have CD19+ diffuse large B-cell, follicular, or mantle cell lymphomas with no available curative treatment options, a limited prognosis of several months to <2 years anticipated survival with currently available therapies, and progressive or relapsed disease after a single intravenous dose of $5 \times 10^8 \pm 20\%$ CTL019/CTL119 administered on our currently enrolling clinical trial (NCT02030834). We anticipate enrollment of 12 total patients onto the present trial for patients not responding to, or relapsing after, CTL019/CTL119.

[figure not shown]
The safety and efficacy of pembrolizumab in this group of patients will be determined using a fixed dose of 200mg IV. This dose was previously well-tolerated and effective for treatment of patients with metastatic melanoma and NSCLC. The primary safety endpoint will be determined by assessing the rate of pembrolizumab discontinuation as well as the rate of occurrence of treatment-related adverse events (AEs), defined as NCI CTCAE version 5 grade ≥ 3 AEs are possibly, probably, or definitely related to study treatment or grade 4 cytokine release syndrome. Secondary efficacy endpoints will be assessed, including overall response rate (ORR) and progression-free survival (PFS).

History (adverse events), physical examination, assessment of performance status, and routine laboratory studies will be performed prior to first pembrolizumab dose and every 3 weeks prior to pembrolizumab administration. Baseline tumor assessment by radiologic imaging will be performed within 6 weeks of starting pembrolizumab and then prior to week 12 after first dose of pembrolizumab, and then should be performed every 12 weeks from most recent imaging PET/CT, CT of chest/abdomen/pelvis, or MRI chest/abdomen/pelvis ± 2 weeks until 24 months after first dose of pembrolizumab. The duration of pembrolizumab administration will be one year; however, we plan to continue data collection regarding: (1) engraftment as long as patients are at risk (until evidence of loss of detectable transduced T cells); (2) disease-free survival until disease progression; (3) survival until time of death; or (4) until the patient withdraws consent for clinical data collection, as part of the follow-up data collection specified for the FDA for gene modified cell therapy clinical trials.

This document is confidential and the property of the University of Pennsylvania. No part of it may be transmitted, reproduced, published, or used by other persons without prior written authorization from the regulatory sponsor.

Peripheral blood, and when possible tumor biopsies, will be obtained prior to pembrolizumab and during therapy with pembrolizumab for correlative studies (see collateral research below).

2.2 Trial Diagram

- Assessment for adverse events every 3 weeks prior to pembrolizumab

3.0 TRIAL OBJECTIVES & HYPOTHESES

3.1 Primary Objectives & Hypotheses

(1) Objective: To determine the safety of pembrolizumab in patients failing to respond to or relapsing after CTL019/CTL119 for relapsed or refractory CD19+ lymphomas.

Hypothesis: Pembrolizumab will be safely tolerated with $\leq 30\%$ of patients experiencing toxicities resulting in discontinuation of pembrolizumab

3.2 Secondary Objectives & Hypotheses

(1) Objective: To describe the overall response rate (ORR) at 3 months to pembrolizumab in patients failing to respond to or relapsing after CTL019/CTL119 for relapsed or refractory CD19+ lymphomas. To describe the clinical efficacy of pembrolizumab, including progression-free survival, disease-free survival, event-free survival, response duration, and overall survival (Cheson, 2007) in patients failing to respond to or

This document is confidential and the property of the University of Pennsylvania. No part of it may be transmitted, reproduced, published, or used by other persons without prior written authorization from the regulatory sponsor.

relapsing after CTL019/CTL119. Efficacy comparisons will be made for ORR between CTL019/CTL119 and pembrolizumab.

Hypothesis: Pembrolizumab will enhance the efficacy of CTL019/CTL119 in patients failing to respond to or relapsing after CTL019/CTL119 for relapsed or refractory CD19+ lymphomas (John, 2013).

- (2) **Objective:** To describe the immunophenotypic and cytokine profiles of chimeric antigen receptor modified T cells in these patients before and after therapy with pembrolizumab

Hypothesis: Immunophenotypic profiles of tumor cells and chimeric antigen receptor modified T cells obtained pre and post pembrolizumab therapy will identify patients for whom pembrolizumab will enhance efficacy.

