1.0 TRIAL SUMMARY

Title	Phase I/II study of pembrolizumab in patients failing to respond to or relapsing after anti-CD19 chimeric antigen receptor modified T cell therapy for relapsed or refractory CD19+ lymphomas
Abbreviated Title	Pembrolizumab after CTL019/CTL119 for relapsed/refractory CD19+ lymphomas
Trial Phase	Phase I / II
Clinical Indication	Relapsed / refractory CD19+ B cell lymphomas after CTL019/CTL119
Trial Type	Investigator-initiated
Type of control	None. Enrollment will be offered to subjects with an unmet medical need, which is no available effective, standard therapy for relapsed / refractory CD19+ lymphomas
Route of administration	Intravenous
Trial drug, dose, route, regimen	Pembrolizumab (Keytruda [®]) 200mg fixed dose IV every 3 weeks
Trial Blinding	None
Treatment Groups	Single group
Number of trial subjects	12 evaluable subjects
Estimated enrollment period	12 months (approximately January 2016-January 2017)
Estimated duration of trial	36 months (approximately January 2016-January 2019)
Duration of Participation	24 months (12 months treatment + 12 months follow-up)
Objectives	
Primary Endpoints:
 
 1. Determine safety of pembrolizumab after CTL019/CTL119. This endpoint will be met if $\leq 30\%$ of patients develop toxicity resulting discontinuation of pembrolizumab. 2. Determine efficacy of pembrolizumab after CTL019/CTL119. This endpoint will be met if the ORR at 3 months is $\geq 35\%$.
Statistical methodology	
Primary Endpoints:
 
 1. Safety endpoint will be assessed using a Bayesian monitoring rule to ensure probability of a patient developing toxicity resulting in discontinuation of pembrolizumab $\leq 30\%$ 
Secondary Endpoints:
 
 1. ORR will be assessed using a one-sided binomial test 2. PFS, EFS, RD, and OS will be assessed using Kaplan Maier survival analysis. PFS after pembrolizumab will be compared to PFS after CTL019/CTL119 using a log rank test.

This document is confidential and the property of the University of Pennsylvania. No part of it may be transmitted, reproduced, published, or used by other persons without prior written authorization from the regulatory sponsor.

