4.2 Rationale

4.2.1 Rationale for the Trial and Selected Subject Population

We are currently conducting a phase IIA clinical trial of redirected autologous T cells, engineered to contain anti-CD19 attached to 4-1BB and TCR ζ signaling domains, in patients with chemotherapy relapsed or refractory CD19+ lymphomas (NCT02030834). Briefly, autologous T cells collected from eligible patients with diffuse large B cell, follicular, and mantle cell lymphomas are transduced using a lentiviral vector to express a chimeric antigen receptor comprised of an extracellular single chain antibody (scFv) with specificity for CD19 in tandem with an intracellular signaling domain comprised of 4-1BB and TCR ζ signaling molecules. The transduced T cells have specificity for cells expressing CD19, a molecule that is restricted in expression to the surface of B cell lymphoma cells as well as normal B cells. Therapy with anti-CD19 chimeric antigen receptor modified T cells has shown efficacy in chronic lymphocytic and acute lymphoblastic leukemias (Porter, 2011; Grupp, 2013; Maude, 2014). On our lymphoma trial, to date, 7 of 7 evaluable patients with relapsed or refractory follicular lymphoma have responded to anti-CD19 chimeric antigen receptor modified T cell therapy (100% response rate and at a median follow-up of 290 days, only one patient has had progression of disease [*[name], preliminary data*]), while only 6 of 12 evaluable patients with relapsed or refractory diffuse large B cell lymphoma have responded to therapy (50% response rate; 5 of 6 patients have ongoing complete responses at median follow-up of 274 days [*[name], preliminary data*]). We have preliminary evidence that the PD-1 receptor-ligand pathway may have a role in patients failing to respond to chimeric antigen receptor

This document is confidential and the property of the University of Pennsylvania. No part of it may be transmitted, reproduced, published, or used by other persons without prior written authorization from the regulatory sponsor.

modified T cell therapy, since we have observed increased expression of PD-1 on CTL019/CTL119 with decreased TNF- α and IFN- γ levels in the setting of progressive disease. This has also been demonstrated in a laboratory model of CAR T cells in combination with PD-1 blockade (John, 2013).

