5.0 METHODOLOGY

5.1 Entry Criteria

5.1.1 Diagnosis/Condition for Entry into the Trial

1. Histologically confirmed follicular lymphoma grade 1-3A, diffuse large B cell lymphoma, or mantle cell lymphoma by WHO 2009 classification
2. Relapsed/refractory lymphoma after CTL019/CTL119
3. No available curative treatment options, a limited prognosis of several months to <2 years anticipated survival with currently available therapies, and progressive or relapsed disease

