5.1.3 Subject Exclusion Criteria

The subject must be excluded from participating in the trial if the subject:

1. Is currently participating and receiving study therapy or has participated in a study of an investigational agent and received study therapy or used an investigational device within 4 weeks of the first dose of treatment. An exception will be made for patients who have received CTL019/CTL119 on experimental protocol; these patients will be eligible to enroll once progression of disease or failure to respond is documented by clinical or radiologic assessment.
2. Patient has received intervening therapy for lymphoma after CTL019/CTL119 infusion.
3. Has active cytokine release syndrome from CTL019/CTL119 infusion.
4. Has a known history of active TB (Bacillus Tuberculosis).
5. Hypersensitivity to pembrolizumab or any of its excipients.
6. Has had a prior anti-cancer monoclonal antibody (mAb) within 4 weeks prior to study Day 1 or who has not recovered (i.e., \leq Grade 1 or at baseline) from adverse events due to agents administered more than 4 weeks earlier. Toxicities that are disease related will not exclude patients.
7. Has had prior chemotherapy, targeted small molecule therapy, or radiation therapy within 2 weeks prior to study Day 1 or who has not recovered (i.e., \leq Grade 1 or at baseline) from adverse events due to a previously administered agent.
 - Note: Subjects with \leq Grade 2 neuropathy are an exception to this criterion and may qualify for the study.
 - Note: If subject received major surgery, they must have recovered adequately from the toxicity and/or complications from the intervention in the opinion of the Principal Investigator prior to starting therapy.
8. Has a known additional malignancy that is progressing or requires active treatment. Exceptions include basal cell carcinoma of the skin or squamous cell carcinoma of the skin that has undergone potentially curative therapy or in situ cervical cancer.
9. Has known active central nervous system (CNS) metastases and/or carcinomatous meningitis. Subjects with previously treated brain metastases may participate provided

This document is confidential and the property of the University of Pennsylvania. No part of it may be transmitted, reproduced, published, or used by other persons without prior written authorization from the regulatory sponsor.

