8.1.2 Secondary Objectives & Hypotheses

Any patient who receives at least one dose of pembrolizumab will be included in efficacy analyses.

(1) Objective: To describe the overall response rate (ORR) to pembrolizumab in patients failing to respond to or relapsing after anti-CD19 chimeric antigen receptor modified T cell therapy for relapsed or refractory CD19+ lymphomas.

Methodology: For efficacy, a sample size of 12 patients achieves an 80% power to detect a difference (P1 0.35 – P0 0.05) of 0.30 using a one-sided binomial test for ORR. The target of significance level is 0.05. This response rate prediction of 35% is based on the reported 28% response rate reported for nivolumab, another anti-PD1 blocking antibody, in patients with B cell lymphoma. This also assumes that a 5% response rate would be seen if pembrolizumab does not have efficacy in this population. If the response rate is 3 or more, the hypothesis that the ORR is ≤ 0.05 is rejected. If the number of responses is 2 or less, the hypothesis that ORR is ≥ 0.35 .

Hypothesis: The response rate after pembrolizumab will be 3 or more, allowing us to reject the null hypothesis that pembrolizumab after CTL019/CTL119 has an ORR ≤ 0.05

(2) Objective: To describe the clinical efficacy of pembrolizumab, including progression-free survival, disease-free survival, event-free survival, response duration, and overall survival (Cheson, 2007) in patients failing to respond to or relapsing after anti-CD19 chimeric antigen receptor modified T cell therapy for relapsed or refractory CD19+ lymphomas. Efficacy comparisons will be made with both most recent prior therapy as well as with CTL019/CTL119.

Methodology: Kaplan Meier survival analysis will be used to estimate progression-free survival, event-free survival, response duration, and overall survival. For patients with initial responses to both CTL 019 and pembrolizumab, progression-free survival, event-free survival, and response duration, patients' response to CTL 019 therapy will be compared to their response to pembrolizumab using the log-rank test, with $p \leq 0.05$ considered statistically significant.

Hypothesis: Pembrolizumab will enhance the efficacy of CTL019/CTL119 in patients failing to respond to or relapsing after chimeric antigen receptor modified T cell therapy for relapsed or refractory CD19+ lymphomas.

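### The planned ORR comparison of pembrolizumab with CTL019/CTL119 is made in patients selected for CTL019/CTL119 failure, so it cannot support the attached hypothesis of enhancement

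*Combined protocol and SAP*

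**What the plan says.** Section 3.2, secondary objective (1), covers ORR at 3 months and the time-to-event outcomes. It adds that "Efficacy comparisons will be made for ORR between CTL019/CTL119 and pembrolizumab". The hypothesis printed under it is that "Pembrolizumab will enhance the efficacy of CTL019/CTL119 in patients failing to respond to or relapsing after CTL019/CTL119".

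Section 8.1.2(1) tests ORR with a one-sided binomial test in 12 patients: 5% under the null, 35% under the alternative, rejection at 3 or more responses. The 5% is the rate assumed if pembrolizumab has no efficacy in this population. The source of the alternative is given: "This response rate prediction of 35% is based on the reported 28% response rate reported for nivolumab, another anti-PD1 blocking antibody". The hypothesis stated for this test is only that an ORR of 5% or less will be rejected.

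Section 8.1.2(2) repeats the enhancement hypothesis and says "Efficacy comparisons will be made with both most recent prior therapy as well as with CTL019/CTL119". Its only comparative method is a log-rank test of time-to-event outcomes in patients who responded to both therapies. No method, pairing or estimand is given for the ORR comparison.

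The setting is fixed by three further entries. The type of control in section 1.0 is "None. Enrollment will be offered to subjects with an unmet medical need". Section 5.1.1 requires "Relapsed/refractory lymphoma after CTL019/CTL119". Section 5.1.3 excludes a candidate if "Patient has received intervening therapy for lymphoma after CTL019/CTL119 infusion".

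**The concern.** To show that pembrolizumab enhances CTL019/CTL119, the trial would have to separate three things: pembrolizumab's own activity, a late response to the CAR T cells without pembrolizumab, and an interaction between the two. A single group treated after CTL019/CTL119 failure cannot separate them.

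The ORR comparison adds a selection problem. Patients still in response to CTL019/CTL119 cannot enter, while non-responders can. The comparator rate in this cohort is simply the share of enrolled patients who first responded and later relapsed. It reflects the enrolment mix and is lower than the rate in all treated patients.

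Because the comparison and the enhancement hypothesis stand under the same objective, a reader of the results would naturally take a favourable ORR difference, or a positive test against 5%, as support for enhancement. Neither can supply it.

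**Working it through.** **Step 1: the plan's own figure.** Inputs from section 8.1.2(1): n = 12, reject at 3 or more responses, p0 = 0.05, p1 = 0.35. The formula is P(X ≥ 3) = 1 − [(1−p)^12 + 12p(1−p)^11 + 66p²(1−p)^10].

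- p = 0.05: 1 − (0.5404 + 0.3413 + 0.0988) = 0.0196, the exact type I error.
- p = 0.35: 1 − (0.0057 + 0.0368 + 0.1088) = 0.849, the exact power.

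With 11 patients and the same cut-off the power is 79.99%, so 12 is the smallest number that reaches 80%. The sample size reproduces.

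**Step 2: what selection does to the comparator.** The inputs are in section 4.2.1. In follicular lymphoma, "7 of 7 evaluable patients with relapsed or refractory follicular lymphoma have responded to anti-CD19 chimeric antigen receptor modified T cell therapy", and one of the seven has progressed. In diffuse large B cell lymphoma, 6 of 12 responded, and 5 of those 6 are in ongoing complete response.

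- All evaluable patients: (7 + 6)/(7 + 12) = 13/19 = 68%.
- Those who would qualify here include the 6 large-cell non-responders and the 1 follicular progressor, who was a responder. The status of the sixth large-cell responder is not given.
- If that patient relapsed: (1 + 1)/(6 + 1 + 1) = 2/8 = 25%.
- If that patient is in an ongoing partial response and so not eligible: 1/(6 + 1) = 1/7 = 14%.
- If only non-responders enrol: 0/12 = 0%.

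The step from 13/19 to 2/8 or 1/7 removes 11 or 12 responders and no non-responders, so the rate can only fall.

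**Step 3: how the comparison would look.** Take the planned pembrolizumab ORR of 35% against each comparator:

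| CTL019/CTL119 ORR used | Difference |
|---|---|
| 68% (all evaluable) | 35 − 68 = −33 points |
| 25% (2/8) | 35 − 25 = +10 points |
| 14% (1/7) | 35 − 14 = +21 points |
| 0% (non-responders only) | 35 − 0 = +35 points |

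The sign changes with selection alone. In the last row, one pembrolizumab response among 12 is enough for a favourable difference. At the 5% rate that the plan equates with no efficacy, that happens with probability 1 − 0.95^12 = 1 − 0.540 = 46%.

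**Step 4: what the test against 5% can say about enhancement.** Suppose pembrolizumab has no effect on the CAR T cells and the true ORR is p, from PD-1 blockade alone or from any other source. At the cited p = 0.28: 1 − (0.0194 + 0.0906 + 0.1937) = 0.696. The 28% is a nivolumab figure in B cell lymphoma; the documents give no PD-1 rate after CAR T failure. The range is therefore shown:

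| True ORR without enhancement | P(3 or more of 12) |
|---|---|
| 5% | 2.0% |
| 10% | 11.1% |
| 15% | 26.4% |
| 20% | 44.2% |
| 25% | 60.9% |
| 28% | 69.6% |
| 35% | 84.9% |

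At the success threshold, 3/12 = 25%, the exact 95% CI is 5.5% to 57.2%. That interval contains 28%, so a result that just meets the rule is compatible with PD-1 activity alone.

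**Step 5: the second comparator.** Section 8.1.2(2) lists the most recent prior therapy beside CTL019/CTL119. Section 5.1.3 excludes lymphoma therapy given between CTL019/CTL119 and pembrolizumab, so read literally the two are the same treatment. They differ only if the phrase means the therapy before CTL019/CTL119.

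**The case against.** The best defence is that the plan claims less than this. Objective 3.2(1) is framed as description. No test, p-value or decision rule is attached to the ORR comparison, so a cross-tabulation would already fit the text. Section 8.1.2(1) gives the binomial test the narrow hypothesis of ORR above 5%. The CAR T cell profiles have their own objective and are treated as exploratory in section 8.1.3. All of this is correct, and it limits the point to the comparison in 3.2(1) and the enhancement wording in 3.2(1) and 8.1.2(2). It does not remove it: the text promises a comparison and prints a directional enhancement hypothesis directly beneath it.

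A reader might infer three stronger things that the documents do not support.

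- That the 5% null is wrong, or that 69.6% is a false-positive rate. It is neither. At a true ORR of 28% pembrolizumab is active, rejecting 5% is correct, and 69.6% is the power. Nor does the SAP name this test as the test of enhancement.
- That eligibility fixes the CTL019/CTL119 response rate. Patients who responded and then relapsed may enrol, so the rate is lowered by selection and depends on the mix.
- That the comparison with most recent prior therapy is void and should be struck out. It may mean the therapy before CTL019/CTL119, the only reading under which the sentence names two comparators.

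The log-rank comparison in 8.1.2(2) does not fill the gap. It concerns time-to-event outcomes and is restricted to patients who responded to both therapies.

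**Conclusion.** The point holds as a mismatch between the stated hypothesis and what the analyses can show. Selection on CTL019/CTL119 failure lowers the comparator from 68% to roughly 14% to 25%, or to 0% if only non-responders enrol, so a favourable ORR difference is partly built in. The test against 5% reproduces and is valid for activity after CTL019/CTL119 failure, but a positive result there carries no information on enhancement as such.

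The selection figures rest on 19 preliminary patients, of whom 7 or 8 would qualify. They assume that this pool is typical, and they include no mantle cell patients, who are eligible but have no response data in section 4.2.1. The 69.6% assumes that the nivolumab rate carries over to this population. The conclusion itself depends on neither number: it follows from the single group, the absence of a control and the entry criteria. Sample size and decision rule are unaffected.

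**What to change.** In sections 3.2(1) and 8.1.2:

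- Restate the efficacy hypothesis as activity of pembrolizumab after CTL019/CTL119 failure (ORR above 5%), and report the ORR with its exact 95% CI.
- Replace the ORR comparison with a descriptive within-patient cross-tabulation of response to CTL019/CTL119 by response to pembrolizumab. State beside it that patients were selected for failure or relapse after CTL019/CTL119 and that the table supports no claim of superiority or enhancement.
- State that most recent prior therapy means the therapy before CTL019/CTL119. If it means CTL019/CTL119 itself, remove it as redundant.
- Leave enhancement to the exploratory CAR T cell correlative measures.

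The cost is a wording amendment. The binomial test, its cut-off, the sample size and the trial procedures stay as they are. The price is a more modest efficacy claim.
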